10.5.2 AE Causality

For unsolicited AEs, the Investigator will determine a causal relationship to the study vaccines and nivolumab.

Missing information regarding relationship to study vaccines or nivolumab, related/not related, will be handled using the worst-case approach. That is, unsolicited AEs with missing relationship to either study vaccines or nivolumab will be considered as "related".

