***“Is there a reasonable possibility that the adverse event may have been caused by the study vaccine?”***

- **YES (related):** There is a reasonable possibility that the study vaccine contributed to the adverse event
- **NO (not related):** There is no reasonable possibility that the adverse event is causally related to the administration of the study vaccine. There are other, more likely causes and administration of the study vaccine is not suspected to have contributed to the adverse event

The Investigator is required to provide an assessment of relationship of AEs to the vaccine or study procedures and determines causality. The Sponsor and local medical monitor can add another causality assessment to the Investigator’s causality. However, the causality given by the Investigator must not be downgraded by the Sponsor or the local medical monitor. If the

Sponsor or the local medical monitor disagrees with the Investigator's causality assessment, the opinion of both the Investigator, the Sponsor and the local medical monitor should be provided with the report.

Every effort should be made by the Investigator to determine the existence of any pre-existing conditions (e.g. headache in adults or rashes in infants on study Day 0 with onset prior to study vaccination) that must be taken into consideration when assessing causal relationship of an adverse event. Pre-existing conditions should be recorded in the eCRF as baseline history and substantiated by appropriate source documentation. Intermittent conditions such as headaches may not be present on study Day 0 but may represent an adverse event if the intensity or duration of the event is worse than usual following study vaccine.

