10.0 Conventions and Derivations

10.1 Treatment Groups

In the outputs, the treatment groups will be labelled as Group 1, Group 2, Group 3 and Group 4, rather than the full description of the first and second vaccinations, in order to conserve space. The definitions of these 4 groups are described in Table 1.

Table 1 Treatment Groups

Treatment Group	1 st Vaccination	2 nd Vaccination
Group 1	MVA-HBV 1 x 10 ⁸ pfu	MVA-HBV 1 x 10 ⁸ pfu
Group 2	ChAdOx1-HBV 2.5 x 10 ¹⁰ vp	MVA-HBV 1 x 10 ⁸ pfu
Group 3	ChAdOx1-HBV 2.5 x 10 ¹⁰ vp	MVA-HBV 1 x 10 ⁸ pfu + Nivolumab 0.3 mg/kg
Group 4	ChAdOx1-HBV 2.5 x 10 ¹⁰ vp + Nivolumab 0.3 mg/kg	MVA-HBV 1 x 10 ⁸ pfu + Nivolumab 0.3 mg/kg

For the safety analysis, the actual treatment groupings are assigned as follows:

- Group 1 = MVA-HBV in 1st vaccination
- Group 2 = ChAdOx1-HBV in 1st vaccination, No Nivolumab in 2nd vaccination
- Group 3 = ChAdOx1-HBV in 1st vaccination, Nivolumab in 2nd vaccination
- Group 4 = ChAdOx1-HBV + Nivolumab in 1st vaccination

The possible combinations of treatments at the first and second vaccinations and the resulting actual treatment group are described in Table 2.

Table 2 Actual Treatment Groups

Randomisation	Actual 1 st Vaccination Given	Actual 2 nd Vaccination Given	Treatment Group Assigned for the Safety Analysis
Group 1	MVA-HBV	MVA-HBV	Group 1
Group 2	ChAdOx1-HBV	MVA-HBV	Group 2

Randomisation	Actual 1 st Vaccination Given	Actual 2 nd Vaccination Given	Treatment Group Assigned for the Safety Analysis
Group 3	ChAdOx1-HBV	MVA-HBV + Nivolumab	Group 3
Group 4	ChAdOx1-HBV + Nivolumab	MVA-HBV + Nivolumab	Group 4
Group 1	MVA-HBV	No vaccination given	Group 1
Group 2	ChAdOx1-HBV	No vaccination given	Group 2
Group 3	ChAdOx1-HBV	No vaccination given	Group 2
Group 4	ChAdOx1-HBV + Nivolumab	MVA-HBV (Nivolumab not given)	Group 4
Group 4	ChAdOx1-HBV + Nivolumab	No vaccination given	Group 4
Group 3	ChAdOx1-HBV	MVA-HBV (Nivolumab not given)	Group 2
Group 4	ChAdOx1-HBV (Nivolumab not given)	MVA-HBV + Nivolumab	Group 3
Group 4	ChAdOx1-HBV (Nivolumab not given)	MVA-HBV (Nivolumab not given)	Group 2
Group 4	ChAdOx1-HBV (Nivolumab not given)	No vaccination given	Group 2

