10.6 Treatment-Emergent Events

Treatment-emergent events are defined as those occurring during or after the first study vaccine administration.

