10.8 Missing Data Values

All statistical analysis will be based on observed values. Apart from handling missing AE relatedness, missing values will neither be replaced, nor estimated.

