12.7.2 Other Safety Endpoints

12.7.2.1 Other Adverse Events

An overall summary of treatment-emergent adverse events, including the number of events reported, will be provided for:

- Any AEs
- Any AEs within 28 days of first vaccination
- Any AEs within 28 days of second vaccination
- Any grade 3 or greater AEs within 28 days of first vaccination
- Any grade 3 or greater AEs within 28 days of second vaccination
- Any AEs related to study vaccines
- Any AEs related to nivolumab

- Any AEs related to study vaccines or nivolumab
- Any grade 3 or greater AEs related to study vaccines
- Any grade 3 or greater AEs related to nivolumab
- Any grade 3 or greater AEs related to study vaccines or nivolumab
- Any AEs with outcome of death
- Any serious AEs
- Any serious AEs related to study vaccines
- Any serious AEs related to nivolumab
- Any serious AEs related to study vaccines or nivolumab
- Any AEs leading to discontinuation of study vaccines
- Any AEs leading to discontinuation of nivolumab
- Any AEs leading to discontinuation of study vaccines or nivolumab
- Any AEs of special interest

Deaths will be identified using the AE eCRF.

In addition, individual summary tables by SOC and PT will be provided for each category (with the exception of any AEs with outcome of death) in the overall TEAE table and presented similarly to the primary endpoint in Section 12.7.1.1. A by-participant summary of all TEAEs leading to death, serious TEAEs, and TEAEs leading to discontinuation of study vaccines or nivolumab will be produced.

AEs leading to discontinuation of study vaccines or nivolumab are defined as any AE with Action Taken with Study Vaccines = 'Drug Withdrawn' or Action Taken with Nivolumab = 'Permanently Discontinue' recorded on the Unsolicited AEs eCRF.

TEAEs will be further summarised by maximum severity (grade 1, grade 2, grade 3, grade 4, grade 5) within each SOC and PT. Participants with multiple events within a particular SOC or PT will be counted under the category of their most severe event within that SOC or PT.

Non-treatment-emergent AEs will be presented by SOC and PT.

All adverse events (including non-treatment-emergent events) recorded on the eCRF will be listed separately.

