16.0 List of DMC and Interim Analysis Outputs

TFL	DMC	Interim
Table 14.1.1.3 Participant Disposition	✓	✓
Table 14.1.2.1 Demographic Characteristics	✓	✓
Table 14.2.1 Summary of HBsAg Geometric Mean by Time Point	✓	✓
Table 14.3.1.1 Summary of Exposure	✓	✓
Table 14.3.2.2 Treatment-Emergent Adverse Events by System Organ Class and Preferred Term	✓	✓
Table 14.3.2.13 Grade 3 or Greater Treatment-Emergent Adverse Events Related to Study Vaccines by System Organ Class and Preferred Term	✓	✓
Table 14.3.2.14 Grade 3 or Greater Treatment-Emergent Adverse Events Related to Nivolumab by System Organ Class and Preferred Term	✓	✓
Table 14.3.2.16 Participants with Treatment-Emergent Adverse Events with Outcome of Death	✓	✓
Table 14.3.2.17 Serious Treatment-Emergent Adverse Events by System Organ Class and Preferred Term	✓	✓
Table 14.3.2.18 Participants Who Experienced Serious Treatment-Emergent Adverse Events	✓	✓
Table 14.3.2.25 Participants Who Experienced Treatment-Emergent Adverse Events Leading to Discontinuation of Study Vaccines or Nivolumab	✓	✓
Table 14.3.2.27.a Solicited Adverse Events by Intensity Grade after each Vaccination	✓	✓
Table 14.3.2.27.b Solicited Adverse Events by Intensity Grade after each Vaccination – Sensitivity Analysis including all data	✓	✓
Table 14.3.2.28 Local and Systemic Reactogenicity by Vaccination and Time Point	✓	✓
Table 14.3.3.1.1 Potentially clinically significant Post-baseline Laboratory Results	✓	✓
Table 14.3.3.2.3 Participants With an Out of Range Haematology Result	✓	✓
Table 14.3.3.3.3 Participants With an Out of Range Biochemistry Result	✓	✓
Table 14.3.4.1 Potentially Clinically Significant Vital Sign Results	✓	
Listing 16.2.1.2 End of Study	✓	✓
Listing 16.2.1.3 End of Treatment	✓	✓
Listing 16.2.7.1 Treatment-Emergent Adverse Events	✓	✓
Listing 16.2.7.2 Solicited Adverse Events (eDiary)	✓	✓
Listing 16.2.7.3 Local and Systemic Reactogenicity	✓	✓

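### SAP 10.5.2 imputes a missing relationship to nivolumab as related even where the participant had not received nivolumab

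*SAP*

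**What the plan says.** SAP 10.5.2 expects two causality judgements for each unsolicited event: "For unsolicited AEs, the Investigator will determine a causal relationship to the study vaccines and nivolumab". It then takes a worst-case approach to gaps: "unsolicited AEs with missing relationship to either study vaccines or nivolumab will be considered as" related. No condition is placed on receipt of nivolumab or on onset relative to an infusion.

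SAP 10.8 confirms that this is a deliberate exception to an otherwise observed-data analysis: "Apart from handling missing AE relatedness, missing values will neither be replaced, nor estimated". SAP 10.6 starts the reporting window at the vaccine, not at nivolumab: "Treatment-emergent events are defined as those occurring during or after the first study vaccine administration".

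The imputed field feeds named outputs. SAP 12.7.2.1 lists rows for any, Grade 3 or greater and serious events related to nivolumab (for example "Any grade 3 or greater AEs related to nivolumab"). It also lists the matching rows for vaccines or nivolumab combined, with tables by system organ class and preferred term behind them. SAP 12.0 presents safety tables by Groups 1 to 4 and Total. SAP 16.0 sends Table 14.3.2.14 ("Grade 3 or Greater Treatment-Emergent Adverse Events Related to Nivolumab by System Organ Class and Preferred Term") to the DMC and the interim analysis.

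On exposure, SAP 10.1 defines the no-nivolumab comparator as "Group 2 = ChAdOx1-HBV in 1st vaccination, No Nivolumab in 2nd vaccination". Group 1 receives MVA-HBV only. Group 3 receives nivolumab with the second vaccination, on Day 28.

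**The concern.** A worst-case rule for missing causality is sensible when the drug could have caused the event and the judgement was not recorded. It is not conservative when the drug had not been given, because the resulting classification is impossible. The SAP recognises only related and not related, and does not say how the nivolumab field is coded for someone who never had an infusion. The causality question in Protocol 8.2.4.2 asks only "Is there a reasonable possibility that the adverse event may have been caused by the study vaccine", with no parallel question for nivolumab and no option for not applicable. Missing nivolumab fields in unexposed participants are therefore possible.

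At stake is the credibility of the attribution tables. A nivolumab-related event could appear in a Group 1 or Group 2 column. In Group 3, an event from the first 28 days could be credited to an infusion that came later. The combined row is also exposed: an event the investigator judged unrelated to vaccine would become related through an empty field for a drug not given.

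**Working it through.** The plan gives no figure on this point to reproduce. The check has three parts.

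**1. Does any other text limit the rule?**

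| Place | Content | Limits the rule? |
|---|---|---|
| SAP 10.5.2 | Missing relationship set to related | No exposure or timing condition |
| SAP 10.8 | Relatedness is imputed, other missing values are not | No |
| SAP 10.6 | Treatment emergence starts at first vaccine | No; pre-infusion events in Group 3 are included |
| SAP 10.1, Table 2 | Assigns actual treatment groups for safety | No; it sets the column, not the causality rule |
| SAP 12.0 and 12.7.2.1 | Related rows, shown for Groups 1 to 4 and Total | No |

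Nothing restricts the imputation to participants or periods with nivolumab exposure.

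**2. How many participants could the rule reach wrongly?**

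Inputs: Group 1 = 10 and Group 4 = 9 (SAP 8.1); Groups 2 and 3 = 16 each, planned (Protocol Table 1); follow-up to Day 273 (SAP Table 3); first nivolumab in Group 3 on Day 28.

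- Total: 10 + 16 + 16 + 9 = 51.
- Never exposed by design: 10 + 16 = 26; 26/51 = 51.0%. With the Protocol's range of 8 to 10 for Group 4, this is 26/50 = 52.0% to 26/52 = 50.0%.
- Unexposed before Day 28: 10 + 16 + 16 = 42; 42/51 = 82.4%.
- Unexposed planned follow-up: 26 × 273 + 16 × 28 = 7,098 + 448 = 7,546 of 51 × 273 = 13,923 person-days, or 54.2%.

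These are shares of participants and of time without exposure. They are not misclassification rates.

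**3. What would the effect be for a given rate of missing fields?**

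The documents give neither the proportion *m* of events with a missing nivolumab field nor the number *k* of unsolicited events per participant. Both are assumed here, with missingness independent between events. The expected number of the 26 never-exposed participants with at least one impossible classification is 26 × [1 − (1 − *m*)^*k*]. With *k* = 3:

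| *m* | 1 − (1 − *m*)^3 | Expected participants of 26 |
|---|---|---|
| 0% | 0 | 0 |
| 2% | 0.059 | 1.5 |
| 5% | 0.143 | 3.7 |
| 10% | 0.271 | 7.0 |
| 100% | 1 | 26 |

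Under the restricted rule proposed below, the count in these 26 is 0 at every value of *m*, provided they received what was planned. Group 3 events shown to precede the infusion also contribute 0.

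**The case against.** The strongest objection is that the effect may never arise. The SAP is to be read with the eCRF, which is not among the documents. The form may record not related or not applicable for unexposed participants, and then nothing is missing. SAP 10.5.2 itself says the investigator determines both relationships. Protocol 8.2.5.3 anticipates nivolumab-related events, and Protocol 9.3 requires edit checks and query resolution before lock. On that view the rule is only a backstop for stray gaps. This stands as a limit on size: a reader might infer that blanks are the normal entry for unexposed participants and that such events are therefore being miscounted, but the documents do not show that. It does not remove the defect, because the rule exists for fields that are missing and gives an impossible answer in these cases.

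A second objection is that little of importance is touched. This also stands in large part. The primary endpoint for vaccines with nivolumab counts adverse events, serious events and Grade 3 or greater events within 4 weeks of dosing, without regard to causality. The summaries in SAP 12.7.1.1 likewise do not use relatedness. The nivolumab-related rows fall under other safety endpoints, safety is descriptive, and no formal Group 3 versus Group 2 safety comparison is specified. A reader might infer that the main nivolumab safety result is biased; the documents do not support that. Table 14.3.2.14 covers only Grade 3 or greater events, and SAP 8.1 describes the interim analysis as already past.

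A third objection concerns the remedy. Setting every pre-infusion or no-infusion event to not applicable would overwrite recorded investigator judgements, which Protocol 8.2.4.2 says must not be downgraded. It could also lose genuine post-infusion events: SAP 10.9.1 sets a fully missing start date to the first vaccination, which would place such a Group 3 event before the infusion. And blanking out planned groups would ignore actual receipt, since SAP 10.1 assigns actual Group 1 from the first vaccination alone. All three points stand, and the fix below is built to meet them.

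**Conclusion.** The point holds as a defect in the stated rule. As written, SAP 10.5.2 would classify an unsolicited event as related to nivolumab whenever that field is missing, including in participants never given nivolumab and, in Group 3, before Day 28. The consequence is confined to the nivolumab-related and combined rows of SAP 12.7.2.1, their supporting tables, and Table 14.3.2.14.

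The size cannot be determined. It runs from nil, if the eCRF leaves nothing missing for unexposed participants, to every unsolicited event in those participants if the field is always blank. The counts of 26 and 42 of 51 rest on planned sizes of 16 for Groups 2 and 3 and on treatment as planned.

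A further stronger reading is that a missing nivolumab field also makes the event vaccine-related, and so reaches the primary endpoint on Grade 3 or greater vaccine-related events. The word *either* leaves room for this, but the text does not state it; the more natural reading imputes only the relationship that is missing. The wording should settle the matter.

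**What to change.** Amend SAP 10.5.2 as follows:

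- Impute each relationship separately, so that a gap in one does not alter the other.
- Impute a missing nivolumab relationship as related only if the participant actually received nivolumab and either onset is on or after the first infusion, or onset is missing or partial and cannot be shown to precede it. Use the reported onset for this test, not the date imputed under SAP 10.9.1.
- Otherwise treat the missing nivolumab relationship as not applicable, and derive the combined row from the vaccine assessment, itself imputed if missing.
- Leave every recorded investigator assessment unchanged.

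Actual receipt and timing come from the infusion records, not from the randomised or planned group. The cost is one added sentence and one programming condition, using infusion dates that SAP 12.5 shows are already on the eCRF. No new data are needed. If the analysis has already been run, Protocol 10.2 provides for documenting and justifying the departure from the SAP in the clinical study report.

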10.5.3 Serious Adverse Events (SAEs)

A serious adverse event (SAE) is defined as any adverse event meeting at least one of the following criteria:

- It results in death (i.e. the adverse event caused or led to the fatality). Serious does not describe an event which hypothetically might have caused death if it were more severe
- It was immediately life-threatening (i.e. the adverse event placed the participants at immediate risk of dying. It does not refer to an event which hypothetically may have led to death if it were more severe)
- It required inpatient hospitalisation or prolonged hospitalisation beyond the expected length of stay. Hospitalisations for scheduled treatments and elective medical/surgical procedures related to a pre-existing condition that did not increase in severity or frequency following receipt of study vaccine, are not serious by this criterion. Hospitalisation is defined as a hospital admission or an emergency room visit for a period greater than 24 hours
- It resulted in a persistent or significant disability/incapacity (i.e. substantial reduction of the participant's ability to carry out activities of daily living)
- It resulted in a congenital anomaly or birth defect (i.e. an adverse finding in a child or foetus of a participant exposed to the study vaccine prior to conception or during pregnancy)
- Other medically important conditions that may not result in death, threaten life or require hospitalisation (i.e. the adverse event does not meet any of the above serious criteria) may be considered an SAE when, based on appropriate medical judgment, they may jeopardise the participant and require medical or surgical intervention to prevent one of the serious outcomes listed in these criteria (e.g. allergic bronchospasm requiring intensive treatment in an emergency room or at home; blood dyscrasias or convulsions that do not result in hospitalisation, or the development of drug dependency or drug abuse)

All criteria leading to an AE being classified as a SAE will be recorded on the eCRF.

10.5.4 Adverse Events of Special Interest (AESI)

An adverse event of special interest (AESI) is an event of scientific and medical concern specific to the Sponsor's product.

These include pneumonitis, grade 3 or 4 diarrhoea, diabetes, thyroid diseases, colitis, nephritis, immune-related endocrinopathies, myocarditis, immune-related skin conditions, or other unspecified immune-related adverse reactions.

All AESI will be identified by investigator assessment, using the AEs listed above as a guideline, and will be recorded on the eCRF.

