#### Primary Endpoints

- Safety and reactogenicity of the vaccine(s): incidence of adverse events, SAEs,  $\geq$ Grade 3 study vaccine-related adverse events within 4 weeks of vaccination
- Safety of the vaccines with nivolumab: incidence of adverse events, SAEs,  $\geq$ Grade 3 adverse events within 4 weeks of dosing
- Incidence of adverse events of special interest (AESIs)
- Number and proportion of participants reporting treatment-emergent adverse events within each treatment group
- Number and proportion of participants within each treatment group with potentially clinically significant laboratory values and vital signs within each treatment group
- Change from baseline in laboratory tests and vital sign measurements to each time point of collection

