### **5.9 Blinding**

This is an open label study; therefore, no procedures for blinding are necessary. The study team members and participant will know the treatment the participant is receiving.

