### **8.3 Events of Special Interest**

Adverse events of special interest in this study are those previously reported with nivolumab in oncology indications requiring dose modification or termination (see SmPC), and prior studies in CHB patients, including the onset of any autoimmune disorder and hepatitis flares. These include pneumonitis, grade 3 or 4 diarrhoea, diabetes, thyroid diseases, colitis, nephritis, immune-related endocrinopathies, myocarditis, immune-related skin conditions, or other unspecified immune-related adverse reactions.

These events will be reported to the Sponsor as for SAEs (see [Section 8.2.5](#)).

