12.7.1.1 Adverse Events

The number and percentage of participants reporting each adverse event, including the number of events, will be summarised by SOC and PT coded according to the MedDRA dictionary. Participants are only counted once within each SOC and PT. AEs will be sorted by decreasing frequency within each SOC and PT according to the overall treatment group.

In addition, summaries will be provided for the subset of AEs, SAEs, and Grade 3 or greater AEs that occurred within 28 days of first vaccination and second vaccination (vaccination day + 27 days) separately.

AESI will also be tabulated by PT for all events occurring during the study.

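### AESI incidence, a primary endpoint, is open to differential ascertainment by group, and the SAP has no treatment-independent AESI count to check it

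*SAP*

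**What the plan says.** Protocol section 2 and SAP 12.7.1 both name AESI incidence as a primary endpoint. SAP 10.5.4 gives the list in one sentence. It begins "These include pneumonitis, grade 3 or 4 diarrhoea, diabetes, thyroid diseases, colitis, nephritis" and continues "immune-related endocrinopathies, myocarditis, immune-related skin conditions, or other unspecified immune-related adverse reactions". It then sets the rule for identification: "All AESI will be identified by investigator assessment, using the AEs listed above as a guideline, and will be recorded on the eCRF".

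Protocol 8.3 describes the source of the events as "those previously reported with nivolumab in oncology indications requiring dose modification or termination (see SmPC), and prior studies in CHB patients". It goes on to name new autoimmune disorders and hepatitis flares, neither of which appears in SAP 10.5.4.

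The trial is open label. Protocol 5.9 says: "The study team members and participant will know the treatment the participant is receiving".

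For analysis, SAP 12.7.1.1 says: "AESI will also be tabulated by PT for all events occurring during the study". SAP 12.7.2.1 adds an AESI line to the overall TEAE summary and a table by SOC and PT. All of these start from the investigator's flag. The SAP describes no MedDRA term list, no adjudication blind to treatment and no sensitivity analysis for AESI.

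**The concern.** The same event may be ticked as an AESI in one participant and left as an ordinary AE in another, and the person ticking knows who received nivolumab. Where the entry itself asks whether the event is immune-related, that knowledge can enter the decision. Protocol Appendix 2 tells investigators that AEs after nivolumab may have an immunological cause and urges early recognition. Its table of immune-related reactions concerns nivolumab only, and there is no matching guidance for participants who receive vaccine alone.

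Two readings of the AESI table are at stake. An excess in Groups 3 and 4 could partly reflect readier flagging. A low count in Groups 1 and 2 could partly reflect a higher threshold for calling an event immune-related, although immune-type events after vaccine alone are a safety question in their own right. With the AESI tables as planned, neither possibility can be checked.

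**Working it through.** **1. The plan's own detection figure.** SAP 8.1 gives an 80% chance of seeing an event of 10% incidence in 16 participants. Check: 1 − 0.9^16 = 0.815, which agrees. The figure concerns severe or serious AEs; the documents state none for AESI. Applied to an AESI, it assumes that every event is recorded as one. If half were flagged, the recorded rate would be 5% and the chance 1 − 0.95^16 = 0.560.

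**2. How much of the list depends on attribution.** The SAP sentence has ten entries. Three carry the immune-related qualifier: endocrinopathies, skin conditions and the open-ended last entry. Seven do not: pneumonitis, grade 3 or 4 diarrhoea, diabetes, thyroid diseases, colitis, nephritis and myocarditis. This counts list entries; it does not give the share of events or participants affected.

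**3. Illustration of unequal flagging.** Recorded rate = true rate × probability of being flagged. Group sizes are 10 and 9 for Groups 1 and 4 (SAP 8.1) and a planned 16 each for Groups 2 and 3 (Protocol 3.2). That gives 16 + 9 = 25 participants in the nivolumab groups and 10 + 16 = 26 in the others. The true rate is set at 10% in every group. The flagging probabilities are assumptions.

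| Flagged, Groups 3+4 | Flagged, Groups 1+2 | Recorded rates | Ratio | Expected participants (of 25 v of 26) |
|---|---|---|---|---|
| 0.9 | 0.9 | 9% v 9% | 1.0 | 2.25 v 2.34 |
| 0.9 | 0.7 | 9% v 7% | 1.29 | 2.25 v 1.82 |
| 0.9 | 0.5 | 9% v 5% | 1.8 | 2.25 v 1.30 |
| 1.0 | 0.25 | 10% v 2.5% | 4.0 | 2.50 v 0.65 |

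The ratio does not depend on the true rate. For true rates of 5% to 20%, and including a 1.0 against 0.5 scenario (ratio 2.0), the spurious difference runs from 1 to 15 percentage points.

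**4. Dilution by the seven unqualified entries.** Suppose only a share s of AESIs falls under the three qualified entries and the rest are flagged at 0.9 in every group. With 0.9 against 0.5 for the qualified share, the ratio is 0.9 / (0.5s + 0.9(1 − s)). For s = 1 this is 1.8. For s = 0.5 it is 0.9/0.7 = 1.29. For s = 0 it is 1.0. The documents do not give s.

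**5. Direction.** If the assumed probabilities are exchanged between the groups, the 1.8 becomes 0.5/0.9 = 0.56. Nothing in the documents measures which way flagging would lean. Appendix 2 makes a lean towards nivolumab recipients plausible, but that is inference.

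**6. Under a common rule.** If one term list is applied to all coded TEAEs, the flagging probability is the same in every group. With flagging of 1.0 and a 10% true rate, the expected counts are 2.5 of 25 and 2.6 of 26, a ratio of 1.0.

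**The case against.** The strongest reply is that unflagged events are not lost. SAP 12.7.1.1 tabulates every AE by SOC and PT in each group whatever was ticked, and SAP 12.7.2.1 adds tables by maximum severity and full listings. A rash in Group 1 therefore appears beside a rash in Group 4. Hepatic and renal signals also have ascertainment that ignores treatment: SAP 12.7.2.3 grades ALT, AST, bilirubin and creatinine from the numeric value alone, and SAP 12.7.1.2 summarises ALT and AST at each visit. Safety analysis is descriptive (Protocol 10.2.2.6), with no AESI test or threshold. Most of this stands. What it does not supply is an AESI incidence: participant counts cannot be added across preferred terms, and no set of terms is fixed in advance, so a reader would have to choose terms after seeing the groups.

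Three stronger readings are tempting and are not supported:

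- A reader might infer that AESI incidence is biased towards the nivolumab groups. No document gives a flagging rate, so this is a risk and not a finding.
- A reader might take the list to be purely one of nivolumab toxicities. Protocol 8.3 also cites earlier studies in chronic hepatitis B.
- A reader might conclude that immune-type events in Groups 1 and 2 will be missed. At most they would be absent from the AESI tables.

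**Conclusion.** The concern holds as a gap in the plan. A primary safety endpoint rests on a judgement made with treatment known, from a mainly nivolumab-derived guideline list, and nothing in the SAP gives an AESI count independent of treatment. The size and direction of any bias cannot be taken from the documents. The ratios of 1.29 to 4.0 rest wholly on assumed flagging rates and equal true rates, and they shrink towards 1.0 as more AESIs fall under the seven unqualified entries. In participants, the gap at a 10% true rate is about half (2.25 v 1.82) to two (2.50 v 0.65). That is small in absolute terms, but one participant is 4 percentage points of 25 and 11 of a group of 9, so one or two flags could make up the whole contrast.

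Separately, SAP 10.5.4 and Protocol 8.3 disagree on autoimmune disorders and hepatitis flares and must be reconciled. This is a cheap improvement and does not call for replacing the endpoint's definition.

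**What to change.** In SAP 10.5.4 and 12.7.1.1:

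- Keep the investigator-flagged AESI table.
- Add a second table of AESI incidence by group, counting participants, from a MedDRA preferred-term list. Apply the list by program to all TEAEs in all four groups whatever the investigator ticked.
- Fix the list before database lock and build it from the dictionary, without reference to by-group listings. This matters because SAP 16.0 includes TEAE tables by SOC and PT among the interim outputs.
- Cover every Protocol 8.3 category, including autoimmune disorders and hepatitis flares, once the SAP list has been reconciled with the protocol. Keep the stated grade 3 or 4 limit for diarrhoea.
- Report the two tables side by side.

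The term list should not replace the investigator's definition. Making every skin, endocrine, cardiac, pulmonary, renal and hepatic term the primary AESI definition would cost specificity and come close to repeating the SOC and PT tables.

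The cost is one term list and one programmed table from AEs that are already to be coded in MedDRA, with no new data collected. The list will pick up some non-immune events in every group, so counts will rise. It corrects unequal flagging but not unequal detection or reporting. Investigators still choose the reported term and which abnormal laboratory results to report as AEs, and the biochemistry panel in Protocol 7.1.4.2 lists neither thyroid function nor blood glucose.
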